### 5.3.1.4. Dose Modification for Adverse Reactions

The dose of ibrutinib/placebo must be modified according to the dose modification guidance in [Table 1](#) and [Table 2](#) if any of the following toxicities occur:

- Grade 4 neutropenia (ANC <500/ $\mu$ L) for more than 7 days. See [Section 6.1](#) for instructions regarding the use of growth factor support
- Grade 3 thrombocytopenia (platelets <50,000/ $\mu$ L) in the presence of clinically significant bleeding events
- Grade 4 thrombocytopenia (platelets <25,000/ $\mu$ L)

- Grade 3 or 4 nausea, vomiting, or diarrhea if persistent, despite optimal anti-emetic and/or anti-diarrheal therapy
- Any other Grade 4 or unmanageable Grade 3 toxicity

Adverse events that are considered related to concomitant high dose corticosteroids (eg, hyperglycemia, insomnia) do not require dose modification or holding of ibrutinib.

For Grade 3 or 4 atrial fibrillation or persistent atrial fibrillation of any grade, consider the risks and benefits of ibrutinib treatment. *If clinically indicated, the use of anticoagulants or antiplatelet agents may be considered for the thromboprophylaxis of atrial fibrillation (Section 6.2.3).*

For other AEs not listed above, including Grade 2 AEs that are deemed per the investigator potentially manageable by dose reduction, these can be managed with a one dose level reduction.

In the event that the investigator feels deviation from the recommendations above is required, please consult the medical monitor to discuss for approval.

If the dose of ibrutinib/placebo is reduced for an adverse event, at the investigator's discretion, the dose of ibrutinib may be re-escalated after 4 weeks of a dose reduction in the absence of a recurrence of the toxicity that led to the reduction. Dose changes must be recorded in the Dose Administration eCRF.

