**8.2.1.4. Week 37, 49, and every 12 weeks thereafter (± 7 days)****Predose**

- Physical examination
- Vital signs
- Performance status (KPS/Lansky) ([Appendix C](#))
- Hematology
- Serum chemistry
- cGVHD activity assessment per NIH ([Appendix H](#) and [Appendix J](#))
- cGVHD response assessment ([Appendix I](#))
- Lee cGVHD Symptom Scale ([Appendix F](#))/SF-36 Questionnaire ([Appendix G](#))
- FEV1 every 12 weeks if prior FEV1 was abnormal, every 24 weeks if prior FEV1 was normal (see [Section 7.1.3.2](#))
- Quantitative serum immunoglobulins (IgA, IgG, and IgM)
- Pharmacodynamic sampling ([Appendix B](#)) (Weeks 49, 73, and 97 only)
- T/B/NK sampling ([Appendix B](#)) (Weeks 37, 49, 73 and 97 only)
- Biomarker sampling ([Appendix B](#)) (Weeks 37, 49, 73 and 97 only)
- Review returned subject dosing diary
- Drug accountability
- Review AEs and concomitant medications (including corticosteroid requirements)

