#### **8.3.1. Response Follow-up**

Subjects who discontinue ibrutinib/placebo for reasons other than progressive cGVHD or progression of underlying malignancy will be followed at pre-specified response assessment time points (Weeks 5, 13, 25 and every 12 weeks thereafter) by clinic visit until progressive disease or progression of underlying malignancy. During this period, the following procedures will be performed:

- Physical examination
- Vital signs
- Performance status (KPS/Lansky) ([Appendix C](#))
- Hematology
- Serum chemistry
- cGVHD activity assessment per NIH ([Appendix H](#) and [Appendix J](#))
- cGVHD response assessment ([Appendix I](#))
- Lee cGVHD Symptom Scale ([Appendix F](#))/SF-36 Questionnaire ([Appendix G](#))
- FEV1 every 12 weeks if prior FEV1 abnormal, every 24 weeks if prior FEV1 normal
- Review corticosteroid requirements and any new cGVHD treatment if applicable

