1.2.2. Secondary Endpoints

- Time to withdrawal of all corticosteroids for treatment of cGVHD
- Time to withdrawal of all immunosuppressants, including corticosteroids for treatment of cGVHD (with the exception of ibrutinib/placebo)
- Response rate at 24 weeks
- Improvement in Lee cGVHD Symptom Scale
- Proportion of subjects who achieve reduction of corticosteroids dose level less than 0.15 mg/kg/d at 24 weeks sustained for at least 30 days
- Overall survival (OS)
- Duration of response (DOR)

Safety

- Safety and tolerability of ibrutinib in combination with prednisone compared to prednisone in combination with placebo.
- Differences in corticosteroids -related morbidities (e.g., hyperglycemia, hypertension)

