5. SAFETY

Safety data will be summarized by arm for the safety population and where appropriate for the pediatric subgroup. Table 3 summarizes the planned safety analyses. Adverse events (AEs) will be coded in accordance with the Medical Dictionary for Regulatory Activities (MedDRA) version 22.1. Severity of AEs will be graded by the investigator according to the NCI-CTCAE v4.03 for hematologic and non-hematological AEs.

The primary analysis will use the ibrutinib/placebo treatment-emergent period, which will include all reported AEs satisfying any of the following criteria:

- Those events that occurred or worsened after the first dose of ibrutinib/placebo, through the treatment phase, and within 30 days following the last dose of ibrutinib/placebo or initiation of subsequent cGVHD systemic therapy, whichever occurred first.
- Events with a missing onset date with a resolution date during the ibrutinib/placebo treatment phase; or
- Events that were considered study drug-related regardless of the start date of the event.

For completeness, an additional analysis will be performed to assess AEs that occurred while the patient was being treated with either component of the study treatment (ibrutinib/placebo and/or prednisone; hereinafter referred to as study treatment AEs) and which will include all reported AEs satisfying any of the following criteria:

- Those events that occurred or worsened after the first dose of ibrutinib/placebo or prednisone, through the treatment phase, and within 30 days following the last dose of ibrutinib/placebo or prednisone, or initiation of subsequent cGVHD systemic therapy, whichever occurred first.
- Events with a missing onset date with a resolution date during the ibrutinib/placebo or prednisone treatment phase; or
- Events that were considered related to either ibrutinib/placebo or prednisone regardless of the start date of the event.

Summaries of treatment emergent AEs (TEAEs) and study treatment AEs will be provided, unless otherwise specified.

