All laboratory values will be converted to and reported as international standard (SI) units. In general, only data from the central laboratory will be summarized and analyzed. All gradable laboratory parameters will be graded using the NCI CTCAE v4.03. Unless otherwise specified, only baseline and post-baseline values collected during the ibrutinib/placebo treatment-emergent period will be included in the safety analysis. Additionally, summary of hematologic toxicity will be provided.

Table 3: Summary of Safety Analyses

Assessment Type	Definition	Methods
Study treatment (ibrutinib/placebo and/or prednisone) adverse events	Study treatment AEs, serious study treatment AEs, Grade 3 or higher study treatment AEs, study treatment AEs related to prednisone, study treatment AEs leading to prednisone treatment discontinuation. Study treatment AEs resulted in death Predefined corticosteroid-associated AEs will be summarized	Descriptive summary statistics and/or listings
Ibrutinib/placebo TEAEs	TEAEs, TE SAEs, Grade 3 or worse TEAEs, Related TEAEs TEAEs leading to treatment discontinuation, TEAEs leading to dose reduction. TEAEs related to corticosteroids, TEAEs leading to corticosteroid treatment discontinuation. TEAEs resulting in death Protocol-defined events of special interest (major hemorrhage) and other safety observations Predefined corticosteroid-associated AEs will be summarized	Descriptive summary statistics and/or listings
Central Laboratory results collected during the ibrutinib/placebo TEAE period	Worst post-baseline toxicity grade for selected CTCAE gradable hematology and chemistry laboratory measurements. Liver function abnormalities.	Descriptive summary statistics and/or listings
Vital Signs collected during the ibrutinib/placebo TEAE period	Blood pressure, heart rate	Descriptive summary statistics and/or listings

AE: adverse event; TEAE= treatment-emergent adverse events as defined in Section 5; SAE= serious adverse event; CTCAE= Common Terminology Criteria for Adverse Events.

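### The SAP confines laboratory and vital-sign summaries to the ibrutinib/placebo window, an unlisted narrowing of Protocol 10.5 that leaves out some glucose and blood-pressure values measured on continuing prednisone

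*SAP*

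**What the plan says.** SAP Section 5 limits laboratory summaries in two ways. One concerns source: "In general, only data from the central laboratory will be summarized and analyzed". The other concerns time. Subject to any stated exception, "only baseline and post-baseline values collected during the ibrutinib/placebo treatment-emergent period will be included in the safety analysis". Table 3 applies the same period to the row headed "Vital Signs collected during the ibrutinib/placebo TEAE period". The section defines that period through its adverse-event rules. It ends 30 days after the last ibrutinib/placebo dose, or at subsequent systemic cGVHD therapy if that comes first.

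For adverse events the SAP adds a second analysis of "AEs that occurred while the patient was being treated with either component of the study treatment". Laboratory values and vital signs get no counterpart.

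Protocol Section 10.5 is wider. Its treatment-emergent period, defined under Adverse Events, runs to 30 days after the later of ibrutinib/placebo or prednisone. It closes sooner only at new therapy for cGVHD or for progression of the underlying malignancy. Under Clinical Laboratory Tests it tabulates the worst grade over the study. It sets no ibrutinib/placebo window for vital signs.

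SAP Section 1 gives the SAP precedence over the protocol, and SAP 1.2 refers the reader to Section 6 for changes. Section 6 lists the added corticosteroid-withdrawal endpoint with its 30-day requirement, and the move of Karnofsky scores to exploratory efficacy. It does not mention the laboratory and vital-sign window.

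On data collection, Protocol Section 8.3.1 reads: "Subjects who discontinue ibrutinib/placebo for reasons other than progressive cGVHD or progression of underlying malignancy will be followed at pre-specified response assessment time points". The procedures listed there include vital signs and serum chemistry, and Protocol 7.1.2.2 puts glucose in the chemistry panel.

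**The concern.** Prednisone has its own stopping rule (Protocol 5.2), so a subject can stop ibrutinib/placebo and stay on prednisone for months. Glucose and blood pressure are still measured in that time, but the SAP leaves them out of its tables once 30 days have passed since the last ibrutinib/placebo dose.

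Two things are at stake. SAP 1.2.2 makes corticosteroid-related morbidity a secondary safety comparison and gives hyperglycemia and hypertension as its examples, and these are the measurements that bear on it. Also, the cut-off depends on when ibrutinib/placebo stops. If one arm stops earlier, more of its steroid period goes unobserved in these tables, and that arm could appear to have less steroid harm.

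**Working it through.** The plan gives no figure for this loss, so there is none to reproduce.

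**Inputs**
- Window: 30 days after the last ibrutinib/placebo dose (SAP Section 5).
- Visits after stopping ibrutinib/placebo: Weeks 5, 13, 25 and every 12 weeks (Protocol 8.3.1). Week *n* Day 1 is 7 × (*n* − 1) days after first dose, so Weeks 5, 13, 25, 37 and 49 fall on days 28, 84, 168, 252 and 336.
- Prednisone: Table 4 reaches zero at Week 24, day 168. The text under the table expects considerable variation. Ends at Weeks 36 and 48 are my assumptions, to show the range.
- Prednisone and ibrutinib/placebo are taken to start on the same day, and no new therapy starts.

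**Formulas**, for ibrutinib/placebo stopping at Week *s* and prednisone ending at Week *e*
- Window closes at W = 7*s* + 30.
- On-prednisone days outside the window = max(0, 7*e* − W).
- On-prednisone visits left out = number of visit days *v* with W < *v* < 7*e*.

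**Worked cases**
- Stop at Week 8: W = 56 + 30 = 86. Week 13 (day 84) is kept, with two days to spare. The next visit is Week 25 (day 168), when the Table 4 dose is zero. Days outside: 168 − 86 = 82. On-prednisone visits left out: none.
- Stop at Week 4: W = 28 + 30 = 58. Week 13 (day 84) is left out. Days outside: 168 − 58 = 110. Visits left out: one.

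**Results** (days outside / visits left out)

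| Ibrutinib/placebo stop | Prednisone ends Week 24 | Week 36 (assumed) | Week 48 (assumed) |
|---|---|---|---|
| Week 4 | 110 / 1 | 194 / 2 | 278 / 3 |
| Week 8 | 82 / 0 | 166 / 1 | 250 / 2 |
| Week 12 | 54 / 0 | 138 / 1 | 222 / 2 |
| Week 16 | 26 / 0 | 110 / 1 | 194 / 2 |
| Week 20 | 0 / 0 | 82 / 0 | 166 / 1 |
| Week 24 | – | 54 / 0 | 138 / 1 |

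The visit count is the relevant measure, because days without a measurement lose nothing. Two details sit at the margin. The End-of-Treatment visit (Protocol 8.2.3) is due on day 30 ± 7 after the last dose, so it is kept at its nominal time but falls outside if done on days 31 to 37. For a Week 8 stop on the Table 4 taper, the combined window would also take in the Week 25 visit, which lies within 30 days of the last prednisone dose.

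**The case against.** The steroid-morbidity objective is already analysed. Protocol 10.5 handles it through adverse events, using Appendix Q terms that include glucose intolerance and hypertension. SAP Table 3 summarizes corticosteroid-associated events in both adverse-event sets, one of which covers prednisone. Safety is descriptive, with no formal testing. Both laboratory limits carry a qualifier. Nothing is left out while a subject remains on ibrutinib/placebo. Subjects who stop for progression of cGVHD or of the malignancy do not enter Response Follow-up, and new cGVHD therapy closes the period in both documents.

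All of this stands, and it keeps the point modest. It does not remove it. A laboratory abnormality becomes an adverse event only if the investigator judges it clinically significant (Protocol 7.1.1.5), so the event tables do not replace graded glucose or measured blood pressure. Nothing in SAP Section 5 makes an exception for either. The closing rule for the second adverse-event set can also be read as ending at the earlier of the two last doses, which conflicts with Protocol 10.5.

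A reader might go further and infer that the central-laboratory rule makes the worst-grade table miss most severe abnormalities. The documents do not support that. The answer depends on an episode length they do not give. With uniform onset and scheduled draws only, a draw falls inside 54% of 14-day episodes in Weeks 1–25. Over Weeks 1–49 the figures are 19% for 7 days, 35% for 14 days and 67% for 28 days. Unscheduled central draws are neither described nor ruled out. Clinically significant abnormalities from any laboratory are recorded as adverse events, and those of Grade 3 or worse are tabulated. Using one laboratory is a defensible choice, and no section shows that local hematology or chemistry results are recorded at all. The bilirubin dose rules might also suggest that liver toxicity is a named ibrutinib risk, but Protocol 1.2.4 does not list it.

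**Conclusion.** The concern holds in a limited form. The SAP narrows the laboratory and vital-sign period relative to Protocol 10.5 without listing the change, and it excludes some collected glucose and blood-pressure values from subjects still on prednisone. On the Table 4 taper at nominal visits, a Week 4 stop loses one on-prednisone visit and stops from Week 8 on lose none. If prednisone lasts to Week 48, the loss is three visits for a Week 4 stop and two for stops at Weeks 8 to 16. These counts assume nominal visit days, a common start date and no new therapy.

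A reader might infer that all glucose and blood pressure on prednisone are discarded, or that a Week 8 stop loses half the steroid-period data (82 of 168 days, 49%). Neither follows. The exclusion starts only after the 30-day extension, and those 82 days contain no scheduled on-prednisone visit. Nor is bias between arms shown: the documents give no stopping rates by arm, so it is a possibility that the cut-off allows. The central-laboratory restriction affects laboratory values only; for blood pressure the window is the whole issue.

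**What to change.** - Add a by-arm summary of worst glucose grade and of blood pressure over the combined study-treatment window. State its end as 30 days after the later of the last ibrutinib/placebo or prednisone dose, or new cGVHD therapy if earlier, so that the wording cannot be read as the earlier dose.
- Keep the existing ibrutinib/placebo-window tables.
- List the change from Protocol 10.5 in SAP Section 6.
- Name the laboratory parameters that Table 3 now calls selected, with glucose among them.

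The cost is SAP wording, programming and a few extra descriptive tables. The data are already collected, and no patient procedure changes.

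Optionally, add a supportive worst-grade table that includes any local or unscheduled values actually recorded. Its use depends on whether such values exist, and several laboratories would contribute to it.

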##### **1.2.4.3. Cytopenias**

Treatment-emergent Grade 3 or 4 cytopenias (neutropenia, thrombocytopenia, and anemia) were reported in subjects treated with ibrutinib. Subjects should be monitored for fever, weakness, or easy bruising and/or bleeding.

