#### *Laboratory*

9. Adequate renal function defined as estimated Creatinine Clearance  $\geq 30$  mL/min (Cockcroft-Gault formula)
10. Adequate hepatic function as defined by:
  - Total bilirubin of  $\leq 1.5$  x ULN (unless of non-hepatic origin or due to Gilbert's Syndrome) or
  - Total bilirubin of  $> 1.5$  x ULN to 3.0 x ULN if due to GVHD
11. Adequate hematological function defined as:
  - Absolute neutrophil count  $\geq 1.0 \times 10^9/L$  and off growth factor support for 7 days
  - Platelets  $\geq 30 \times 10^9/L$  and no transfusion for 7 days
12. PT/INR  $< 1.5$  x ULN and PTT (aPTT)  $< 1.5$  x ULN (unless abnormalities are unrelated to coagulopathy or bleeding disorder). When treated with warfarin or other vitamin K antagonist, then INR  $\leq 3.0$  ([Section 6.2.3](#)).

---

*Ethical/Other*

13. Male and female subjects of reproductive potential who agree to use both a highly effective methods of birth control (eg, implants, injectables, combined oral contraceptives, some intrauterine devices [IUDs], complete abstinence, or sterilized partner) and a barrier method (eg, condoms, cervical ring, sponge, etc.) during the period of therapy and for 90 days for both females and males after the last dose of study drug.

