## **10.5. Safety Analysis**

Analysis of safety data will be conducted on the safety population, which includes randomized subjects who receive at least 1 dose of ibrutinib/placebo. The baseline value is defined as the last value collected on or prior to the first dose date of ibrutinib/placebo, whichever comes first.

The safety variables to be summarized include exposure to ibrutinib/placebo and prednisone, AEs, clinical laboratory test results (hematology and chemistry), Karnofsky/Lansky performance status, and vital sign measurements. In general, safety data will be tabulated or listed. No formal statistical testing is planned.

Growth and development and late effects will be summarized in adolescent subjects.

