### **Clinical Laboratory Tests**

Laboratory tests will be summarized separately for hematology and serum chemistry. All laboratory values will be graded using the NCI CTCAE v4.03. The worst toxicity grade during the study will be tabulated.

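### Laboratory toxicity is tabulated as worst post-baseline grade without comparison to baseline grade, so Grade 3 platelets and raised bilirubin permitted at entry can count as on-treatment toxicity

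*SAP*

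**What the plan says.** SAP Section 5, Table 3, summarises central laboratory results as "Worst post-baseline toxicity grade for selected CTCAE gradable hematology and chemistry laboratory measurements", using descriptive statistics and/or listings. Protocol Section 10.5 (Clinical Laboratory Tests) has the same approach: "The worst toxicity grade during the study will be tabulated".

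Baseline is not absent from the plan. Protocol Section 10.5 states: "The baseline value is defined as the last value collected on or prior to the first dose date of ibrutinib/placebo". SAP Section 5 states that "only baseline and post-baseline values collected during the ibrutinib/placebo treatment-emergent period will be included in the safety analysis". But no planned laboratory summary says how the baseline grade is to be used. Two further outputs are named without being defined: a line for liver function abnormalities in Table 3, and a haematology summary ("Additionally, summary of hematologic toxicity will be provided").

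The entry criteria in Protocol Section 4.1 allow abnormal values. Criterion 11 sets the platelet floor at 30 x 10^9/L "and no transfusion for 7 days". Criterion 10 allows total bilirubin above 1.5 and up to 3.0 x ULN when GVHD is the cause. Protocol Section 5.3.1.4 gives the platelet cut as "Grade 3 thrombocytopenia (platelets <50,000" per µL, with Grade 4 below 25,000/µL.

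**The concern.** A worst post-baseline grade measures how abnormal a subject was on treatment. It measures toxicity only if subjects start at a low grade, and here some need not. Protocol Appendix M lists thrombocytopenia and raised liver tests among the features of cGVHD, and the dosing table in Protocol Section 5.3.1.5 has a separate column for subjects who enter with raised bilirubin, so such subjects are expected.

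Cytopenias are a named risk of the drug: "Treatment-emergent Grade 3 or 4 cytopenias (neutropenia, thrombocytopenia, and anemia) were reported in subjects treated with ibrutinib" (Protocol Section 1.2.4.3). Readers will look to the laboratory table for the systematic view of that risk. If pre-existing abnormalities are counted in both arms, each absolute rate is too high and the ratio between arms is too close to 1. The SAP's main adverse event criterion counts events that began or got worse after the first dose. The laboratory table has no counterpart to that condition.

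**Working it through.** **Plan's own figure.** The documents give no figure for the laboratory analysis. The sample size of 186 (SAP Section 1.4) belongs to the primary endpoint and is not touched by this point. It reproduces: for 30% vs 50%, two-sided 5%, 80% power, n per arm = [1.96·√(2·0.4·0.6) + 0.8416·√(0.3·0.7 + 0.5·0.5)]² / 0.20² ≈ 93, total 186.

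**Step 1: does eligibility overlap the grades?** Setting the entry limits (Protocol Section 4.1) against the cuts in Protocol Sections 5.3.1.4 and 5.3.1.5:

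| Measure | Allowed at entry | Cut in the protocol | Overlap |
|---|---|---|---|
| Platelets, Grade 3 | ≥30 x 10^9/L | <50 x 10^9/L | Yes: 30 to <50 |
| Platelets, Grade 4 | ≥30 x 10^9/L | <25 x 10^9/L | None |
| Neutrophils, Grade 4 | ≥1.0 x 10^9/L | <0.5 x 10^9/L | None |
| Bilirubin, lower band | up to 3.0 x ULN if due to GVHD | >1.5 to 3 x ULN | Yes |
| Bilirubin, upper band | up to 3.0 x ULN if due to GVHD | >3 x ULN | None, apart from non-hepatic or Gilbert's elevations, which criterion 10 exempts |

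The bilirubin bands are the protocol's dosing bands. The documents do not print CTCAE grade limits for bilirubin, so for bilirubin I claim only that an elevation can be present at entry. No baseline overlap is shown for haemoglobin, ALT, AST or alkaline phosphatase.

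**Step 2: the effect on the table.** Let b be the share of each arm that is already at Grade 3 at baseline and has at least one post-baseline value still there. Because the table takes the worst value over repeated visits, one such value is enough. Let p be the rate of new Grade 3 or higher events among the rest. Then

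tabulated rate = b + (1 − b)·p.

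Both b and p are assumptions. With p = 5% (placebo) and 15% (ibrutinib), the true ratio is 3.00 and the true difference is 10.0 points.

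| b | Placebo | Ibrutinib | Tabulated ratio | Tabulated difference (points) |
|---|---|---|---|---|
| 0% | 5.0% | 15.0% | 3.00 | 10.0 |
| 2% | 6.9% | 16.7% | 2.42 | 9.8 |
| 5% | 9.8% | 19.3% | 1.97 | 9.5 |
| 10% | 14.5% | 23.5% | 1.62 | 9.0 |
| 20% | 24.0% | 32.0% | 1.33 | 8.0 |

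For example, at b = 5%: placebo 0.05 + 0.95 × 0.05 = 9.75%; ibrutinib 0.05 + 0.95 × 0.15 = 19.25%; ratio 1.97.

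**Step 3: the same data counted as worsened from baseline.** The rates become (1 − b)·5% and (1 − b)·15%. The ratio is 3.00 for every b. The difference, (1 − b)·10 points, equals the tabulated difference. What the planned table loses is therefore the ratio and the correct absolute level. The difference is almost intact.

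**The case against.** The case against giving this much weight is strong on several counts.

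- **Other tables have a worsening rule.** The main adverse event criterion requires onset or worsening after the first dose, and Grade 3 or worse events are tabulated. Protocol Section 7.1.1.5 requires laboratory abnormalities that the investigator judges clinically significant to be recorded as adverse events. SAP Table 1 adds a safety subgroup by hepatic impairment. These safeguards are real but partial: adverse event entry depends on investigator judgement, and there is no subgroup by baseline platelets.
- **An entry floor is not a prevalence.** Nothing in the documents says how many subjects enter at 30 to <50 x 10^9/L, and nothing supports a value as high as b = 20%. This stands, and the table above is an illustration only.
- **Absolute grade matters.** Protocol Section 5.3.1.4 ties action to absolute platelet and neutrophil thresholds, so the worst grade reached is safety information in its own right. This stands, and it argues against replacing the planned table or restricting its denominator.

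A reader might also infer more than the documents support. One inference is that the whole cytopenia and liver signal is diluted, but overlap is shown only for Grade 3 platelets and the lower bilirubin band. Another is that the comparison is tilted toward ibrutinib, but assignment is randomised and double-blind, so carry-over is equal in expectation and only a chance baseline imbalance could move it. A third is that the plan ignores baseline altogether. It does not: baseline is defined and included in the data, and the content of the haematologic toxicity summary is simply unstated. Finally, quoting lost power would be misplaced, because Protocol Section 10.5 plans no formal testing of safety data.

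**Conclusion.** The point holds in a limited form. Followed as written, the laboratory table would report a stable, pre-existing Grade 3 platelet count, or a bilirubin elevation already present at entry, as on-treatment toxicity. Absolute rates rise in both arms and the ratio moves toward 1. The size cannot be determined from the documents. It depends on the share of subjects carried over and on the true event rates, both assumed here and taken as the same carry-over in each arm. On the ratio scale the effect is noticeable even at 2% carry-over; on the difference scale it is small. Grade 4 platelets and bilirubin above 3 x ULN are largely unaffected. No endpoint, decision rule or error rate depends on the table. This is an inexpensive improvement to safety reporting, not a flaw in the trial's main inference.

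**What to change.** Keep the worst post-baseline grade table and add to SAP Table 3, by arm:

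1. A shift table of baseline grade by worst post-baseline grade for platelets, neutrophils, haemoglobin, bilirubin, ALT, AST and alkaline phosphatase, using the baseline definition in Protocol Section 10.5.
2. The number and percentage of subjects whose worst post-baseline grade is above their baseline grade, split by worst grade so that new Grade 3 and Grade 4 results can be read directly.

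Define the haematologic toxicity summary and the liver function abnormalities line, and apply the same two displays to them.

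The cost is SAP wording and a few additional standard tables. Haematology and chemistry are already drawn at Screening and on Day 1 and read centrally, so no new data are needed. The change touches no dosing or clinical rule.
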